**A) "Hypercaloric fructose diet group"**

Subjects will be instructed to drink 990 ml of a beverage sweetened with 7.6 % fructose per day while consuming a self-selected *ad libitum* (usual) diet. No advice is given to reduce the energy content of their usual diet. Subjects will be in positive energy balance and therefore subjected to a weight gain of up to 2.5 kg in the 3 month study period. The subjects will be followed by the trained dietitian 6 weeks after the study to ensure that the subjects return to a BW of maximum 1 kg above their baseline BW.

i Helsinki University plans to perform a kinetic study as an extension of the main study. The aim of the substudy is to elucidate the effects of fructose diet on lipoprotein metabolism using stable isotopes. This substudy replaces study visit 3 and is described on page 9.

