### **Power calculations**

Primary endpoints in the current study are 1) change in plasma triglyceride (TG) area under curve (AUC) between the NTG and HTG during fructose feeding (between groups) and 2) change in TG AUC in HTG subjects during isocaloric fructose vs. hypercaloric fructose feeding (within group). The calculations are based on following assumptions: TG AUC increases from 7 to 10.5 mmol/l×hrs in normotriglyceridemic and from 7-9 to 14 mmol/l×hrs in hypertriglyceridemic subjects during fructose. Standard deviation is assumed to be 4.3 based on previous studies in similar groups of patients. 1) To detect significant difference (>3.5 mol/l×hrs) between the groups ( $n=25$ ) with unpaired t-test. 2) To detect significant increase (>3.5 mol/l×hrs) within the group ( $n=15$ ) with paired t-test. These calculations assume that alpha = 0.05 and power = 0.80 in all tests.

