**Studies 2-5 for screen positives are performed twice: before and at the end of the three month diet period.**

### **2. Lipolytic enzymes and genetic studies**

**2.1** Subjects will receive 75 IU/kg heparin *i.v.* to determine lipoprotein lipase and hepatic lipase masses and activities.

**2.2** A blood sample for DNA extraction is drawn. Single nucleotide polymorphisms (SNPs) in genes involved in regulation of lipid metabolism, insulin resistance, inflammation or oxidative stress will be analyzed using Taqman and Sequenom methods. In addition, among hyper- and hyporesponders to fructose, expression quantitative trait loci (eQTL) analysis will be performed comparing mRNA transcript levels and their changes during the intervention from adipose tissue biopsies and relating this to genetic variation.

**2.3** Since diet may lead to low-grade inflammation and insulin resistance due to changes in gut microbial community, the subjects will also provide a stool sample (using specific tubes and instructions) for analysis of gut microbiota profile (future analysis) and answer a health questionnaire. A blood sample for lipopolysaccharide (LPS) and angiopoietin-related protein 4 (Angptl4/fait) analyses is drawn for future analyses.

**2.4** The questionnaire of physical activity is done twice: before fructose period and during weeks 10-12

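### The randomised diet contrast in HTG men is tied to a paired within-group t-test, which cannot compare two parallel arms; a between-arm ANCOVA with baseline TG AUC and centre would answer it

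*Protocol*

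**What the plan says.** The Power calculations section defines both primary endpoints as changes in TG AUC. The first compares NTG with HTG men. The second is the "change in TG AUC in HTG subjects during isocaloric fructose vs. hypercaloric fructose feeding (within group").

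It names one test for each:
- For the first: "To detect significant difference (>3.5 mol/l×hrs) between the groups", n=25, "with unpaired t-test".
- For the second: "To detect significant increase (>3.5 mol/l×hrs) within the group", n=15, with a paired t-test.

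The common inputs are: "Standard deviation is assumed to be 4.3 based on previous studies in similar groups of patients"; and "These calculations assume that alpha = 0.05 and power = 0.80 in all tests".

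Experimental diets states that eligible subjects are randomised to one of two diet groups for 12 weeks. Nobody receives both diets. The study design section has four centres enrolling 32 men each, 128 in all.

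The oral fat load is one of the repeated studies: "Studies 2-5 for screen positives are performed twice: before and at the end of the three month diet period". A baseline TG AUC is therefore planned for every man. Helsinki runs a kinetic visit instead: "This substudy replaces study visit 3 and is described on page 9". The substudy section says that the same fat load is served there, with tracers added and sampling times shown in its own figure.

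The protocol mentions neither baseline TG AUC nor centre as a covariate, and rules out neither.

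**The concern.** The isocaloric vs hypercaloric comparison is the only randomised contrast among the primary endpoints. It is also the one that separates weight-dependent from weight-independent effects of fructose, which is a stated aim. Calling it within-group and giving it a paired test leaves that question without a valid test. Both arms drink fructose, so TG AUC may rise in both, and a significant rise in one arm or in each says nothing direct about the difference.

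The sample size has the same gap. The figure of 15 relates to a rise from baseline, and no between-diet difference is stated anywhere.

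Once the contrast is treated as between-arm, the remaining choice is whether to use the baseline value and centre. Both are already recorded, and the outcome is noisy (SD 4.3 against a target of 3.5).

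**Working it through.** **Inputs.** From Power calculations: difference 3.5, SD 4.3, alpha 0.05, power 0.80, n=25 (unpaired) and n=15 (paired). The target lines print mol; I read mmol, as in the assumptions. Not stated: whether 4.3 is the SD at one visit or of the change, the correlation rho between baseline and end TG AUC, the HTG share, the allocation ratio and any stratification. These are assumed below where needed.

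**1. Reproducing the plan.** The standardised effect is 3.5/4.3 = 0.81.
- Unpaired, two-sided noncentral t: 24.7, so 25 per group (power 80.5%). This matches. One-sided gives 19.4, so 20, and does not.
- Paired, with 4.3 as the SD of the change: 13.9, so 14; power is 83.4% at 15. This is close to the stated 15.

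**2. What the paired test answers.** Suppose both diets raise TG AUC by exactly 3.5 and each arm has 15 men. Each within-arm test is significant with probability 0.834. The chance that one is significant and the other is not is 2 × 0.834 × 0.166 = 0.28. Reading such a split as a diet effect would mislead in more than a quarter of trials in which the diets do not differ.

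**3. The contrast as a two-arm comparison.** Take 3.5 as the between-diet difference (assumed) and 4.3 as the SD of the change.

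| Men per arm | Power | Difference detectable at 80% power |
|---|---|---|
| 15 | 57.6% | 4.56 |
| 25 | 80.5% | 3.48 |
| 32 | 89.3% | 3.06 |

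Thirty-two per arm follows if half of the 128 men are HTG and allocation is 1:1 (both assumed): 128/2/2 = 32.

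**4. What baseline adjustment gains.** Let k be the end/baseline SD ratio.
- Variance of the change, in baseline-variance units: 1 + k² − 2·rho·k.
- ANCOVA residual variance: k²(1 − rho²).

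With k = 1 the ratio of ANCOVA to change-score variance is (1 + rho)/2:

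| rho (assumed) | Ratio | n per arm, change vs ANCOVA, 4.3 = SD of change | n per arm, change vs ANCOVA, 4.3 = SD at one visit |
|---|---|---|---|
| 0.5 | 0.75 | 24 vs 18 | 24 vs 18 |
| 0.7 | 0.85 | 24 vs 21 | 15 vs 13 |
| 0.9 | 0.95 | 24 vs 23 | 5 vs 5 |

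(Normal approximation.)

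With k = 1.5 (assumed; the protocol's NTG mean rises from 7 to 10.5, a factor of 1.5, and the SD may rise with it):
- rho 0.5: 2.25 × 0.75 / (3.25 − 1.5) = 1.6875/1.75 = 0.96
- rho 0.6: 2.25 × 0.64 / (3.25 − 1.8) = 1.44/1.45 = 0.99
- rho 0.7: 2.25 × 0.51 / (3.25 − 2.1) = 1.1475/1.15 = 1.00

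**5. Centre.** If centre explained 5%, 10% or 20% of the variance (assumed), adjusting for it would take n per arm from 24 to 23, 22 or 19.

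For NTG vs HTG, a centre whose changes are shifted by s biases the contrast by s × (its share of the HTG men − its share of the NTG men). Purely as illustration, take 64 men per phenotype, with Helsinki supplying 24 HTG and 8 NTG. Then s = 1 gives 1 × (24/64 − 8/64) = 0.25, and s = 2 gives 0.5, which is 14% of 3.5. With 16 and 16, or with s = 0, the bias is zero.

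**The case against.** The strongest reply is that this is a power section, not an analysis section. Sizing a trial on a t-test does not commit it to an unadjusted analysis, and covariates are commonly left to the SAP. That stands: the absence of baseline and centre terms is not an error in itself, and naming them is an improvement. It does not excuse the paired test, because the protocol itself attaches that test and that sample size to the between-diet endpoint.

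Four stronger readings are tempting, and the protocol does not support them:
- **A raw two-sample change-score t-test is planned for the diet arms.** No such test is written. The unpaired test belongs to NTG vs HTG.
- **Ignoring baseline wastes a known amount of precision.** A saving such as a quarter of the variance needs equal SDs at both visits and rho near 0.5. Neither is given, and step 4 shows the gain can almost vanish.
- **Helsinki's different visit biases the comparisons.** Its men receive the same meal and, taking the second kinetic visit to be at the end of the diet, the same procedure both times. A constant shift in level cancels in each man's change. A proportional shift, for example from different sampling times, would not cancel, but the sampling figure is not available to show whether there is one. In the randomised contrast, centre adds noise or chance imbalance, not systematic bias.
- **The trial is too small for the diet contrast.** The 15 is not the planned enrolment. Under the assumptions in step 3 there could be 32 per arm.

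**Conclusion.** The point holds as a mismatch between endpoint and test: a paired within-group test cannot compare two parallel randomised arms, and the stated n=15 does not size that comparison. This follows from the protocol's own text and needs no assumption. The size depends on taking 3.5 as the between-diet difference and 4.3 as the SD of the change: 25 per arm are then needed, and 15 per arm has 57.6% power.

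Baseline and centre adjustment is a low-cost improvement whose benefit cannot be computed from the protocol. The variance ratio against an unadjusted change score is 0.75 to 0.95 for rho 0.5 to 0.9 with equal SDs, and 0.96 to 1.00 for rho 0.5 to 0.7 with an SD ratio of 1.5. ANCOVA is never materially worse. Centre can confound NTG vs HTG only if both the HTG share and the change in TG AUC differ by centre, and the protocol gives no sign of the size of either.

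**What to change.** 1. Drop the within-group label and the paired test for the second primary endpoint. Define it as the difference between the isocaloric and hypercaloric arms in HTG men, analysed by ANCOVA of end-of-diet TG AUC with baseline TG AUC and centre as covariates.
2. State the between-diet difference to be detected, say what the SD of 4.3 refers to, and give the number of HTG men per arm.
3. For NTG vs HTG, keep the change in TG AUC as outcome and adjust for centre and diet. Do not add baseline TG AUC as a covariate there, because the groups are defined by triglyceride level and differ at baseline by construction.
4. If paired tests of the rise within each arm are still wanted, present them as descriptive.

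The cost is analysis wording and about 4 degrees of freedom in the diet model (1 for baseline, 3 for four centres). No new data are needed.

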### **Inclusion criteria**

Male subjects with body mass index (BMI) 27-40 kg/m^2, waist >96 cm will be recruited. The weight must have been stable (+/- 1 kg during the last 6 months). Each participant will undergo a physical examination and laboratory tests to exclude hepatic diseases (other than hepatic steatosis) and renal, thyroid and hematological abnormalities. Subjects with total cholesterol <6.2 mmol/l, serum triglycerides <5.0 mmol/L, BMI <40 kg/m^2, non-smoking and regular daily alcohol consumption less than 2 doses (*i.e.*, 5 g pure alcohol, maximum alcohol consumption is 2 portions per day or 14 portions per week) are included to the study. Any lipid medication (indicated for primary prevention) or other medication known to affect lipid levels is discontinued at least a month before the screening visit and reintroduced after the completion of the study. Type 2 diabetes is excluded with an oral glucose tolerance test.

Exclusion criteria: Age < 20 years or >65 years, BMI or lipid levels outside the inclusion range, smoking, alcohol consumption over 2 doses/day, type 2 diabetes, cardiovascular disease, hormonal therapy, any chronic disease requiring medication except for controlled hypertension.

The reasons for focusing on males are two-fold: previous studies demonstrate an effect of gender to fructose feeding. Furthermore, as there are major gender differences in body fat distribution, visceral and ectopic fat deposition (women having, on average less visceral and liver fat than men), the study size in a study with both men and women would have been forced to be significantly larger. This wouldn't be compatible with the budget limitations for this grant application. However, the gender difference to fructose feeding is exceedingly interesting and our goal is to perform a follow-up study with both males and females. That study will be designed by the results from this study.

**Study visits** The number of visits is about 3-5 depending on the local circumstances to allocate imaging studies; the kinetic study will have a separate schedule for visits.

Please see specific instructions in excel: Clinical data files\_040612 and Fructose\_sample handling\_fatload\_ogtt\_heparin\_TIMEPOINTS\_040612 and Fructose Fat load bleeding schedule 040612.

Record all results of patients included to study in: **Fructose\_data\_040612**.

### **1. Screening**

Subjects will undergo physical examination (cardiorespiratory status, blood pressure, BMI, waist-hip-ratio and recording of their medical history. A blood sample is drawn after an overnight fast.

**1.1** The screening measures: serum triglycerides, LDL cholesterol and HDL cholesterol, blood count, creatinine, sodium, potassium, thyroid stimulating hormone, glucose, and liver enzymes.

**1.2** An oral glucose tolerance test (see below).

**Studies 2-5 for screen positives are performed twice: before and at the end of the three month diet period.**

### **2. Lipolytic enzymes and genetic studies**

**2.1** Subjects will receive 75 IU/kg heparin *i.v.* to determine lipoprotein lipase and hepatic lipase masses and activities.

**2.2** A blood sample for DNA extraction is drawn. Single nucleotide polymorphisms (SNPs) in genes involved in regulation of lipid metabolism, insulin resistance, inflammation or oxidative stress will be analyzed using Taqman and Sequenom methods. In addition, among hyper- and hyporesponders to fructose, expression quantitative trait loci (eQTL) analysis will be performed comparing mRNA transcript levels and their changes during the intervention from adipose tissue biopsies and relating this to genetic variation.

**2.3** Since diet may lead to low-grade inflammation and insulin resistance due to changes in gut microbial community, the subjects will also provide a stool sample (using specific tubes and instructions) for analysis of gut microbiota profile (future analysis) and answer a health questionnaire. A blood sample for lipopolysaccharide (LPS) and angiopoietin-related protein 4 (Angptl4/fait) analyses is drawn for future analyses.

**2.4** The questionnaire of physical activity is done twice: before fructose period and during weeks 10-12

### **3. Oral fat load study**

After a 12-h fast, subjects will receive a mixed meal consisting of bread, butter, cheese, low fat milk and tea or coffee (63 g carbohydrates, 56 g fat (P/S ratio 0.11), 39.9 g protein) in the morning. Blood samples are drawn before and up to 8 hours after the meal. During this time only water will be served *ad libitum* and the subjects will remain physically inactive.

To study *de novo* lipogenesis during postprandial period the subjects will receive deuterated water ( $^2\text{H}_2\text{O}$ ) 2 g per kg body weight. In the evening before the oral fat load study a blood sample (background sample) (Taken DURING PRECEEDING week before: see sample handling) will be drawn. The subjects will sip deuterated water (2 dl) between 18.00 and 22 hrs together with 5 dl of mineral water.

**3.1** Blood samples (For all sampling: please see Excel: Fructose\_sample handling\_fatload\_ogtt\_heparin\_TIMEPOINTS\_040612 and Fructose Fat load bleeding schedule 040612) are taken the night before (background serum sample) for DNL analysis and before and during the fat load. Lipoprotein fractions will be isolated using density gradient ultracentrifugation.

Concentrations of lipids, apolipoproteins, other biochemical variables will be performed in whole plasma and/or chylomicron (Sf > 400), VLDL1 (Sf 60-400) and VLDL2 (Sf 20-60) fractions. Analysis will include:

- 3.1.1 Triglycerides, cholesterol, apo-B100, apo-B48, markers of energy balance (FFA,  $\beta$ -OHB), glucose and insulin are studied in PLASMA.
- 3.1.2 Enrichment of deuterated water to measure DNL in TRL- fractions are measured.
- 3.1.3 Apo-CIII, apo-A5, uric acid, markers of inflammation (high-sensitive CRP, TNF- $\alpha$ , interleukin-6) are measured. Samples for other biomarkers (serum amyloid A [SAA], IL-8, paraoxonase [PON1], myeloperoxidase [MPO], monocyte chemotactic protein-1 [MCP-1]), markers of coagulation activity (plasminogen activator inhibitor-1) and incretins (glucagon-like peptide-1 [GLP-1] and gastric inhibitory polypeptide [GIP]) are collected for future analyses.
- 3.1.4 Lipidomics profiling utilizing the state of the art GC/MS technology to map a large and comprehensive spectrum of lipid and lipid intermediate species including SCD desaturation index (*i.e.*, the ratio of 16:1n-7/16:0 that is used as an index of SCD enzyme activity) and their responses to diets in serum and VLDL fractions are measured at two time points.
- 3.1.5 Fasting samples: apo-B, apo-AI, apo-AII, adiponectin, ghrelin, leptin, LDL size and HDL size.
- 3.1.6 Needle fat biopsies from subcutaneous abdominal fat are taken fasting and 4 hrs postprandially. Adipose tissue mRNA levels will be profiled to detect which genes are upregulated vs. downregulated in response to fructose and how this relates to genetic variation.
- 3.1.7 Four spare samples (two plasma and two serum samples) of each time-point.
- 3.1.8 In fasting state and during the postprandial period (0 and 4 hrs) blood pressure measures will be performed using a standardized system (BP Tru 200 manometer) and heart rate variability will be tested by ECG recording.

#### 4. Determination of liver, subcutaneous and intra-abdominal fat

On a separate visit the amount of liver, subcutaneous and visceral fat are determined. Proton magnetic resonance spectroscopy is performed with a 1.5 T whole-body device to determine liver fat content. Magnetic resonance imaging is used to determine subcutaneous abdominal and intra-abdominal fat as previously described. A standardized protocol will be used at all centers.

#### 5. Oral glucose tolerance test

An oral glucose tolerance test (For all sampling: please see Excel: Fructose\_sample\_handling\_fatload\_ogtt\_heparin\_TIMEPOINTS\_040612) will be performed in the morning after an overnight fast at screening as well at the end of the 3 month diet period. Sampling time will be at 0, 5, 10, 30, 60, 90, 120, 180 and 240 minutes for determination of glucose, insulin, C-peptide and gut incretins to allow modeling oral glucose insulin sensitivity index (OGIS).

#### SUMMARY:

1. Measurements of routine laboratory lipid and biomedical parameters will be centralized and workload allocated to the expertise of the centers (Helsinki, Laval, Gothenburg, and Naples).
2. DNL measurements and lipidomic analyses will be done in Gothenburg ([name]).
3. SNP genotyping by Taqman and Sequenom and adipose tissue mRNA profiling by Affymetric microarray will be performed in Malmö ([name]).
4. Studies of microbiota will be performed in Gothenburg ([name] [name]).

[figure not shown]
#### Substudy (in Helsinki)

##### Kinetic protocol visit (replacing study visit 3)

This study will replace study visit 3 and is performed before and at 3 months after the diet period. The aim of the study is to elucidate the effects of fructose diet on triglyceride and apo-B non-fasting kinetics using stable isotopes. We will use d3-leusine to study apo-B kinetics and d5-glycerol to study triglyceride kinetics. Simultaneously, hepatic DNL is calculated from enrichment of deuterated water ingested during the kinetic study. The study outline is shown in **figures 5 and 6**. Study subjects will consume  $^2\text{H}_2\text{O}$  during the kinetic protocol as described in visit 3. At 8:00 the subjects will receive a bolus injection of  $^2\text{H}_3\text{-leucine}$  (7 mg/kg) and  $^2\text{H}_5\text{-glycerol}$  (500 mg) as in our previous kinetic protocol. The subjects will be served an oral fat load described in Visit 3. **Urine samples of minimum 100 ml will be collected in the morning of**

**kinetic protocol visit and 4 hours after serving the mixed meal. The urine samples will be used to measure the microvesicles containing multiple protein and nucleic acid classes (mRNA, miRNA, siRNA).**

Dietary triglyceride tracers will be administered through test meal served as outlined in Figure 6 and containing 1,2,3,4-C16-palmitate (1-2 g). Blood samples are drawn according to the figure 6 (red dots). Other biochemical, physiological, lipid and apolipoprotein analysis are done as described in visit 3.

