**Experimental diets**

Subject eligible for the study **will be randomly assigned to one of the two diet groups for 12 weeks:**

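### The protocol gives two conflicting times for the follow-up fat load in Helsinki: at the end of the diet, or three months after it

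*Protocol*

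**What the plan says.** Protocol, Experimental diets: men "will be randomly assigned to one of the two diet groups for 12 weeks". Elsewhere the protocol calls the same period three months.

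Protocol, line introducing studies 2 to 5 (just above section 2, Lipolytic enzymes and genetic studies): these studies, which include the oral fat load of section 3, "are performed twice: before and at the end of the three month diet period".

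Protocol, Substudy (in Helsinki), Kinetic protocol visit: the visit takes the place of visit 3 and "is performed before and at 3 months after the diet period". The same section serves the visit 3 fat load at this visit and takes over the other visit 3 lipid analyses. The footnote on the Helsinki extension confirms the substitution: "This substudy replaces study visit 3 and is described on page 9".

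Protocol, Power calculations: the first primary endpoint is the "change in plasma triglyceride (TG) area under curve (AUC) between the NTG and HTG during fructose feeding (between groups". The second is the change in TG AUC in hypertriglyceridaemic (HTG) men under isocaloric versus hypercaloric fructose feeding.

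Protocol, Study visits paragraph (under Inclusion criteria): the kinetic study has its own visit schedule, which is not given there.

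**The concern.** For one centre, the fat load has two follow-up times. One is on diet. The other, read literally, falls about three months after the beverages stop. The Helsinki sentence is the only timing written specifically for the kinetic visit, and that visit is said to have its own schedule. A reader in Helsinki therefore cannot assume that the general rule prevails.

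The fat load matters because it is the only test described that yields a postprandial TG AUC. The Power calculations section does not name the test, so this link is an inference, though a strong one given the study's focus on postprandial lipaemia.

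Under the literal timing, Helsinki values would reflect wash-out instead of response to fructose. For the hypercaloric group, the protocol states: "The subjects will be followed by the trained dietitian 6 weeks after the study", with the aim of bringing weight back close to baseline. By three months the weight difference between the diets should have largely gone, which blurs the second primary contrast. The VLDL kinetics come only from this visit, so all of them would be off diet, against the substudy's own aim.

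**Working it through.** **1. The two timings side by side**

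| Source | Visit | Follow-up time | On diet? |
|---|---|---|---|
| Line introducing studies 2 to 5 | Oral fat load (study 3) | End of the diet period | Yes |
| Helsinki substudy section | Kinetic visit replacing visit 3, same fat load | Three months after the diet period (literal) | No |
| Power calculations | TG AUC | During fructose feeding | Yes |

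**2. Does anything decide between them?** The Study visits paragraph defers to a separate schedule that it does not give. The substudy refers to figures that are not shown, and sampling details sit in external spreadsheets. The visible text leaves the conflict open.

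**3. How many men?** Each of four centres enrols 32, so 32/128 = 25%. The protocol does not say that every Helsinki man enters the substudy, so 25% is the maximum.

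**4. The plan's own sample sizes.** Inputs from Power calculations: difference 3.5, SD 4.3, alpha 0.05, power 0.80. Two-sided testing is assumed. Power is taken from the noncentral t distribution.

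- Unpaired, n = 25 per group: noncentrality = 3.5 / (4.3 × √(2/25)) = 2.88 on 48 df, power 80.5%. With 24 per group it is 78.8%, so 25 is reproduced.
- Paired, n = 15: noncentrality = 3.5 / (4.3/√15) = 3.15 on 14 df, power 83.4%. With 14 it is 80.4%, so 15 is adequate.

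**5. Illustration of the literal reading.** Let p be the share of men measured off diet and r the fraction of the effect still present then. Neither is in the protocol. Assume p is the same in the groups compared and that the SD is unchanged. The expected contrast is

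3.5 × [1 − p(1 − r)].

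For p = 0.25 and r = 0 this is 3.5 × 0.75 = 2.625. At 25 per group the noncentrality is 2.625 / (4.3 × √(2/25)) = 2.16. At 64 per group it is 2.625 / (4.3 × √(2/64)) = 3.45.

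| p | r | Contrast | Power, 25 per group | Power, 64 per group | Power, paired n = 15 |
|---|---|---|---|---|---|
| 0.25 | 0 | 2.63 | 56% | 93% | 60% |
| 0.25 | 0.50 | 3.06 | 69% | 98% | 73% |
| 0.25 | 0.75 | 3.28 | 75% | 99% | 79% |
| 0.125 | 0 | 3.06 | 69% | 98% | 73% |
| any | 1 | 3.50 | 81% | above 99% | 83% |

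The 64 per group column assumes that all 128 men split evenly into normotriglyceridaemic (NTG) and HTG, which the protocol does not state. The paired column uses the plan's own test for its second calculation.

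**The case against.** The strongest case against is that the wash-out reading is not what the authors meant. The hypercaloric diet section treats the three-month diet as the study period itself and describes only one later contact, at six weeks. A tracer study three months after the diet would fall outside everything else described. The visit replaces an end-of-diet visit, its aim is to show the effect of the fructose diet, and wash-out or reversibility is mentioned nowhere. The phrase reads naturally as one with a missing comma: at three months, after the diet. The figures not shown, or the external schedules, may also settle the timing.

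Most of this stands, and it makes loose drafting the likelier explanation. It does not remove the conflict, because probable intent is not an instruction and a visit held at the wrong time cannot be repeated.

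A reader might infer more: that the primary endpoint will mix on-diet and off-diet values for a quarter of the men, and that the trial's power will fall to 56%. The documents do not support that. Off-diet values arise only if the Helsinki sentence is followed literally, a quarter is a ceiling, and 56% combines complete loss of effect with 25 men per group, although 128 men are planned.

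**Conclusion.** The contradiction is real and concerns the visit from which the TG AUC would come in Helsinki. Followed literally, the substudy wording would put up to 32 of 128 values, and all VLDL kinetic results, outside the period in which the endpoints are defined. The main harm would be bias and a mixed estimand: centre would be confounded with time of measurement, and the contrasts could shrink towards zero to the extent that the effect fades after the diet.

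Loss of power is secondary and uncertain. For the first endpoint with 25% of men fully off diet it would be 56% at 25 per group and about 93% at 64 per group. If the effect were retained in full, there would be no loss. The stated sample sizes of 25 and 15 are not in error and stand once the timing is settled.

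The point rests on the fat load being the source of the primary TG AUC, which is inferred, and on no unseen figure or schedule having already resolved the timing. Even if one has, the sentence itself needs correcting.

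**What to change.** Reconcile the line introducing studies 2 to 5 with the Helsinki substudy section. State one follow-up time, defined relative to the last day of fructose, that applies to visit 3 and to the kinetic visit replacing it in every centre, and that agrees with an endpoint measured during fructose feeding. Any separate schedule for the kinetic study should repeat that time.

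The cost is one sentence, with no extra visit or participant. A general rule to keep Helsinki data out of the pooled analysis is not needed: whether a value belongs depends on when the man was actually measured, and the visit date set against the last day of fructose shows that.
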